The study sites for this study are MUSC general medicine, endocrine, family medicine, and community primary care clinics. The investigative team has access to patients in these clinics and letters of support from key physician collaborators in each of these clinics are attached.

Patient eligibility criteria: The study inclusion and exclusion criteria are as follows

Inclusion Criteria: 1) Age ≥ 21 years; 2) Clinical diagnosis of T2DM and HbA1c $\geq 8\%$ at the screening visit; 3) Self-identified as AA; 4) Subject must be willing to use the FORA monitoring system for 12 months; 5) Subjects must be able to communicate in English; and 6) Subjects must have access to a telephone (landline for data uploads) for the study period.

Exclusion Criteria: 1) Mental confusion on interview suggesting significant dementia; 2) Participation in other diabetes clinical trials; 3) Alcohol or drug abuse/dependency; 4) Active psychosis or acute mental disorder; and 5) Life expectancy <12 months.

Description of Intervention: Patients will be assigned the FORA 2-in-1 Telehealth System and provided glucose test strips to allow testing at least once a day. The glucose and BP readings will be used to tailor and reinforce behavior change during weekly telephone-delivered diabetes education sessions. Subjects will receive: 1) the FORA system for self-monitoring; 2) weekly telephone-delivered diabetes education/skills training; 3) patient activation; and 4) patient empowerment. The intervention will be delivered by telephone once a week for 12 weeks with each session lasting ~ 30 minutes.

Assessments: Patients will be assessed at baseline, 3-months, 6-months, 9-months, and 12-months post randomization. Assessments will include valid and reliable scales administered by the study team. Participants will receive \$25 for completing each visit.

Patient Randomization: A permuted block randomization method will be used to assign subjects to one of the two intervention groups. Block size will be varied to minimize the likelihood that the blind will be broken. The randomization will be stratified by clinical site, and baseline HbA1c levels (8-10% vs. $>10\%$).

Sample Size and Power. With 80 subjects randomized to each of the two intervention groups, we will have 85% power to detect at least a 0.4 standardized effect size (difference in comparison group means in sd units) for continuous outcome measures.

Analysis Plan

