We will use a generalized linear models (GLMM) approach as the general analytic framework for inferential analyses for the Primary/Secondary efficacy aims. In addition to accommodating a wide range of distributional assumptions [dichotomous/categorical (e.g., binomial), continuous (e.g., normal), ordinal, count (e.g., Poisson)]. GLMM is equivalent to a linear mixed effect model (MEM) approach. MEM analyses estimate individual change in outcome for each subject in addition to estimating average change in outcome within each of the individual a, b, c, d intervention groups. The basic modeling procedure will involve using the longitudinal measurements of HbA1c (primary) separately as the dependent (outcome) variable, with intervention group (fixed effect), time (random effect), and time by intervention as the primary independent variables.

Project Timeline: The study duration is four years (48 months). Months 1-6 will be used for startup, Months 7-30 will be used for participant enrollment and intervention delivery, Months 31-42 will be used for participant follow-up and Months 43-48 will be used for data analysis. We will randomize 200 patients in 4 cohorts of 50 patients every 6 months with an average of 9 randomized patients per month.

PROTECTION OF HUMAN SUBJECTS

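### Free improvement: adjust the HbA1c model for baseline HbA1c, on which randomization is stratified, and make the 12-month difference the tested contrast

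*Protocol*

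**What the plan says.** All places are in the Protocol, under Research Strategy.

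- **Approach:** 200 patients, 100 per arm; the primary outcome is HbA1c at month 12.
- **Patient Randomization:** "The randomization will be stratified by clinical site, and baseline HbA1c levels", with the HbA1c strata 8-10% and above 10%.
- **Assessments:** "Patients will be assessed at baseline, 3-months, 6-months, 9-months, and 12-months post randomization".
- **Analysis Plan:** the repeated HbA1c values form the response of a basic model, whose terms are given as follows: "with intervention group (fixed effect), time (random effect), and time by intervention as the primary independent variables". The same section explains that "MEM analyses estimate individual change in outcome for each subject". It names no baseline covariate, no site or stratum term and no 12-month contrast.
- **Sample Size and Power:** "With 80 subjects randomized to each of the two intervention groups, we will have 85% power" for a 0.4 SD difference.
- **Timing of the intervention:** "The intervention will be delivered by telephone once a week for 12 weeks", while an inclusion criterion reads "Subject must be willing to use the FORA monitoring system for 12 months".

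**The concern.** Baseline is one of the five scheduled visits, so in the model as named it can enter only as the first repeated response. With a group main effect and no stated constraint, the baseline means are free to differ between arms. The balance forced by stratifying on HbA1c is then not credited in the standard error.

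The named terms also leave open which quantity is tested. Three natural readings are the raw 12-month difference, the change from baseline to month 12, and a linear group-by-time slope. The last is suggested by the emphasis on individual change and by time being called random. A slope answers the 12-month question only if the effect grows in a straight line. The protocol makes another shape plausible, because the weekly calls stop after 12 weeks while monitoring continues for 12 months.

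At stake is mainly efficiency: power and interval width for the primary endpoint, and whether the primary test matches that endpoint whatever the shape of the effect.

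**Working it through.** **Inputs from the Protocol:** n = 100 per arm (80 in the power statement), effect 0.4 SD, visits at 0, 3, 6, 9 and 12 months.

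**Assumed, not in the Protocol:** two-sided 5% level, complete data, equal correlation ρ between visits (0.3 to 0.6), SD 1 at every visit. The last is relaxed in step 4.

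**1. The plan's own figure.** An unadjusted comparison with 80 per arm and 0.4 SD has 71.0% power (noncentral t), not 85%. A one-sided 5% test gives 81.2% (normal approximation). Baseline adjustment would reach 85% with 80 per arm at ρ of about 0.545, but the Protocol does not say that it relies on this. The mismatch is a separate matter.

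**2. Formulas.** Power comes from the noncentral t with noncentrality Δ/√(2V/n):

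- Raw 12-month difference: Δ = 0.4, V = 1.
- Change from baseline: Δ = 0.4, V = 2(1−ρ).
- Baseline-adjusted 12-month difference: Δ = 0.4, V = 1−ρ².
- Slope over 12 months: weights (t − 0.5)/0.625 at t = 0, 0.25, 0.5, 0.75, 1, so V = (1−ρ)/0.625. Δ = 0.4 if the effect grows linearly. If it is complete by month 3 and then constant, Δ = 0.4 × 0.5/0.625 = 0.32, which is 80% of the 12-month difference.

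**3. Power with equal SD, 100 per arm (%).**

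| Test | ρ=0.3 | 0.4 | 0.5 | 0.6 |
|---|---|---|---|---|
| Raw 12-month | 80.4 | 80.4 | 80.4 | 80.4 |
| Change | 66.2 | 72.9 | 80.4 | 88.2 |
| Slope, linear effect | 75.8 | 81.9 | 88.2 | 94.0 |
| Slope, complete by month 3 | 56.7 | 63.2 | 71.1 | 80.4 |
| Baseline-adjusted | 83.9 | 86.7 | 90.1 | 94.0 |

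The gain over the raw difference is 3.5 to 13.6 points. At ρ = 0.7 the linear-effect slope is slightly ahead (98.2 against 97.6). With 80 per arm the raw test has 71.0%, and the adjusted test 75.0, 78.3, 82.7 and 88.2%.

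**4. Allowing for entry at HbA1c of 8% or more.** The cut trims baseline but not follow-up, so baseline SD and the in-trial correlation both fall. Example: a normal baseline cut at its mean, pre-selection correlation 0.5.

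- Baseline variance: 1 − 2/π = 0.363. Month-12 variance: 1 − 0.25 × 0.637 = 0.841.
- In-trial correlation: 0.5 × 0.363/√(0.363 × 0.841) = 0.33. SD ratio k: √(0.363/0.841) = 0.66.
- Change: V = 1 + k² − 2ρk = 1.00, power 80.4%, the same as raw.
- Adjusted: V = 1 − 0.33² = 0.89, power 84.6%.
- Slope: V = (0.8 − 0.16 × 0.637)/0.841 = 0.83. Power is 87.1% for a linear effect and 69.5% if complete by month 3.

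Over cuts from −0.5 to +0.5 SD and pre-selection correlations of 0.4 to 0.8, the adjusted contrast gains about 1 to 7 points over change and about 5 to 19 over the early-plateau slope. Against a linear-effect slope it ranges from level (83.7 against 83.6) to about 4 points behind.

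**5. Type I error under stratified permuted blocks (simulation, equal SD, 4 sites, 40% in the upper stratum, 10,000 trials per cell), ρ = 0.3 / 0.4 / 0.5 / 0.6.**

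- Raw: 4.2 / 3.8 / 3.3 / 2.6%
- Change: 2.7 / 3.3 / 3.4 / 3.8%
- Random slope: 3.4 / 3.7 / 4.0 / 4.2%
- Adjusted for baseline, site and stratum: 5.0 to 5.3%

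Over all settings run, these three unadjusted readings gave roughly 2.5 to 4.8%. The cause is visible at ρ = 0.5: the raw test reports a standard error of 0.141 when the true value is 0.130, while the adjusted model reports 0.122 against 0.123.

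**6. What site and stratum add.** Simulated power is 84.5 / 87.2 / 90.5 / 94.3% with them and 84.3 / 86.9 / 90.4 / 94.3% with baseline alone.

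**The case against.** **Covariates and contrasts belong in the SAP.** The section describes a basic procedure and lists primary variables, which does not exclude others. This stands to the extent that nothing here is a contradiction. A reader might infer that the trial was to be analysed without baseline HbA1c; the document does not show that. But the Protocol does state a model, and the stated model has a better replacement at no cost.

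**The equal-SD figures overstate the loss.** This stands. The entry cut lowers the baseline SD, so the 18-point deficit of change at ρ = 0.3 (83.9 − 66.2) should not be quoted alone. A reader might also infer that the adjusted contrast is always the most powerful. It is not: with a linearly growing effect and the entry cut, the slope test is level or slightly ahead. In that case the argument for the 12-month contrast is that it tests the stated endpoint whatever the effect shape.

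**Conservative tests do no harm to validity.** This holds for the raw, change and random-slope readings. A reader might extend it to a general assurance against false positives, which the text does not support, because it does not say how a random time effect is to be fitted. In simulation a slope test with only a random intercept rejected a true null in 13 to 19% of trials (correlation 0.7 down to 0.3). With no fixed time term and a 0.1 SD decline shared by both arms, the rate was about 22% in 135 runs. Nor may one infer that such inflation will occur, since the Protocol commits to neither fit.

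**Conclusion.** The point holds as a free improvement to the stated model. Adjusting for baseline HbA1c never did worse than the raw or change contrast in the settings checked.

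With equal SDs and correlations of 0.3 to 0.6 it gains about 4 to 14 points of power over the raw 12-month difference. Allowing for the entry cut, its advantage is about 1 to 7 points over change and 5 to 19 over a slope test when the effect is complete early. It has no power advantage over a slope test when the effect grows linearly. It also brings the type I error from roughly 2.5-4.8% to about 5% under the three readings examined. Nearly all the gain comes from baseline HbA1c; site and stratum add about 1 point or less.

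The sizes rest on assumed correlations, effect shapes, test level and truncation, none of which the Protocol gives. The direction against the raw and change contrasts does not depend on their exact values.

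**What to change.** In the Analysis Plan, specify the primary HbA1c model as follows:

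- Months 3, 6, 9 and 12 are the responses, with continuous baseline HbA1c as a covariate whose slope may differ by visit. An equivalent choice keeps baseline as a response with a common mean constrained across arms.
- Visit is a fixed categorical effect, with group by visit.
- Clinical site and the HbA1c stratum are included as randomization factors.
- The between-group difference at month 12 is the primary test.

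Use the same form, with the corresponding baseline value, for continuous secondary outcomes.

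The cost is one or two sentences. Every variable is collected at or before randomization, so no patients, visits or measurements are added. The change should be fixed before outcome data are examined by arm.

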1. RISKS TO THE SUBJECTS

a. Human Subjects Involvement and Characteristics

The overarching aim of this proposal is to test the efficacy of a technology-intensified diabetes education/skills training (TIDES) intervention in AAs with poorly controlled T2DM. 200 patients will be randomly assigned to two groups of 100 patients each; TIDES intervention group and usual care group. Each patient will be followed for 12 months, with study visits at baseline, 3, 6, 9, and 12 months. The primary outcome will be HbA1c at 12 months post-randomization while the secondary outcomes will be blood pressure control and quality of life at 12 months post-randomization.

Study clinics: The study sites for this study are MUSC general medicine, endocrine, family medicine, and community primary care clinics.

Participant Payment: Randomized participants will receive \$50 for completion of baseline, 3, 6, 9, and 12 month assessments for a total payment of \$250. Those considered ineligible at baseline will receive \$10 and not be randomized.

Patient eligibility criteria: The study inclusion and exclusion criteria are as follows

Inclusion Criteria: 1) Age ≥ 21 years; 2) Clinical diagnosis of T2DM and HbA1c $\geq 8\%$ at the screening visit; 3) Self-identified as AA; 4) Subject must be willing to use the FORA monitoring system for 12 months; 5) Subjects must be able to communicate in English; and 6) Subjects must have access to a telephone (landline for data uploads) for the study period.

Exclusion Criteria: 1) Mental confusion on interview suggesting significant dementia; 2) Participation in other diabetes clinical trials; 3) Alcohol or drug abuse/dependency; 4) Active psychosis or acute mental disorder; and 5) Life expectancy <12 months.

b. Sources of Materials

1. Research Material & Data: Sources of research material include medical history, research questionnaires, blood pressure readings, and blood specimens. The questionnaires will obtain information about demographics, clinical history, diabetes self-care, resource use, depression, and quality of life. Patients will provide ~ 10 cc of blood for laboratory testing.

2. Linkages to Subjects: Subjects will provide identifying information in addition to research data. Paper documents pertaining to this study will be stored in locked file cabinets in both the clinical center and the data management center, and data will be entered into secure, password-protected web databases developed for this study. A database of name, contact address, telephone number, and other research identification numbers will be stored separate from the study database, for purposes of audit by the sponsor (NIH) and MUSC IRB, if necessary. Access to study data will be limited to research personnel.

3. Collection of Data and Specimens:

Personnel: Two full-time masters-level trained diabetes educators (DEs) will deliver the interventions; two full-time research assistants (RAs) will conduct screening, consent, enrollment procedures, and questionnaire administration; a full-time data entry clerk (DC) will be responsible for data entry; and a part-time masters-level statistician will be responsible for data management (DM).

c. Potential Risks

Potential risks to the patient include possible violation of the patient's privacy, discomfort with questions on the research questionnaire, discomfort and bleeding from blood draws, discomfort with BP measurement, and psychological distress. Details on how these risks will be minimized are discussed under adequacy of protection against risks below.

2. ADEQUACY OF PROTECTION AGAINST RISKS

a. Recruitment and Informed Consent

We will use two complementary approaches to identify eligible study subjects. The first method will consist of systematic identification of AA patients with T2DM. After obtaining IRB approval for a partial waiver of HIPAA, we will use clinic-billing records over the previous 12-month period to identify AA subjects with ICD-9 codes consistent with a diagnosis of type 2 diabetes. The PI will share the goals of the study and inclusion/exclusion criteria with physicians and clinic staff during clinic administrative meetings. Physicians and clinic staff will be asked to refer appropriate subjects to the study research assistants. In addition, IRB approved recruitment flyers will be posted in prominent locations in the study clinics.

b. Protection against Risk

A. Patients will be protected against potential risks as follows:

1. Psychological Distress: Because we will be administering a questionnaire that measures the presence of depression, we will take several steps to ensure the safety of all research participants. RAs will be trained by the PI to identify patients who meet criteria for depression on the PHQ-9. Subjects' who screen positive for depression will be notified during the visit and verbally instructed to seek care from their primary health care provider (PCP). They will also be given the 24-hour MUSC crisis psychiatry telephone service and told to call if they experience acute worsening of symptoms before they can be seen by their PCP.

2. Venipuncture (blood drawing): To reduce the risks of discomfort and bruising, venipuncture will be performed by trained personnel. To reduce the risk of fainting, blood will be drawn while subjects are in a seated position. The amount of blood that will be drawn, approximately 10cc, is not considered to pose a health risk for most adults. .

3. Blood Pressure Measurement: To lessen any associated risks, blood pressure measurements will be performed only by trained personnel utilizing a standardized protocol. Subjects with elevated blood pressure will be evaluated by our designated medical monitor and referred to their primary care provider. Those with potentially life threatening blood pressure readings will be sent to a local emergency room for treatment.

4. Administration of Research Questionnaires: Some participants might be offended by detailed questions about emotional or physical health status and impairment, and healthcare utilization. All participants will be informed at the outset that they may terminate participation at any point. Our past research suggests that data collection using these measures can be conducted without undue psychological distress or exacerbation of symptoms among study participants.

5. Unknown risks: Subject participation in research may have other unknown risks. The researchers will advise subjects if they learn of emerging information that might alter subjects' decisions to participate in this study.

B. Subjects requiring medical or other professional intervention for study-related events will be provided with appropriate and timely medical guidance by the designated medical monitor. The medical monitor will have oversight on medical risks and will review all adverse events and report them to the IRB in accordance with the MUSC IRB Adverse Event Reporting Policy. The results of subjects' clinical assessments will be available within a few days of their study visit. The medical monitor will review and advise subjects of these results by phone and, at their request; will also advise their personal physician of the results.

C. To protect against the potential risk of loss of confidentiality and/or breach of privacy, data will be compiled using codes in lieu of personal identifiers. Access to study data will be limited to research personnel. Development of and security oversight for the electronic database for this study will be performed by the study statistician. Paper documents pertaining to this study will be stored in locked file cabinets and electronic data will be entered into secure, password-protected databases developed for this study by the research assistants. The PI will perform periodic review of the data entry process to ensure accuracy of recording. When study results are published or presented, only aggregate reports of the results will be used and participants' identity will not be revealed. A file of name, contact address, telephone number, and other research identification numbers will be stored separately on paper and on computer, for purposes of audit by the sponsor (NIH) and MUSC IRB, if necessary.

3. POTENTIAL BENEFITS OF THE PROPOSED RESEARCH TO THE SUBJECTS AND OTHERS

The intervention is expected to benefit patients, by increasing their knowledge of diabetes, activating and empowering them to better care for their diabetes, improving blood glucose and blood pressure control, and reducing their risk of developing complications of diabetes.

4. IMPORTANCE OF KNOWLEDGE TO BE GAINED

The proposed study is innovative for a variety of reasons. First, sophisticated information technology, such as the FORA system, offers the potential to address several of the barriers to effective care by providing reinforcement and positive feedback to patients that should increase adherence. Second, the culturally-tailored education and skills training intervention proposed in this study is innovative because it targets patient level factors for which there is strong evidence of differences between AAs and Whites with T2DM (i.e. diabetes knowledge, self-management skills, empowerment, and fatalism/perceived control)

5. DATA AND SAFETY MONITORING PLAN

The data and safety monitoring plan will include an internal Data Safety Monitoring Committee (DSMC), a Data and Safety Monitoring Board (DSMB), and the institutional IRB. The purpose of the DSMC, DSMB, and IRB are to ensure the safety of participants and the validity and integrity of the data. Summaries of adverse events reports or patient safety concerns raised by the DSMB or IRB will be made to NIH in the yearly progress unless the nature of a particular event is such that it bears reporting to NIH immediately.

DSMC: The internal DSMC will consist of the PI, biostatistician, co-investigators/consultants on the proposal, and a designated medical monitor. The functions of the DSMC will include: 1) provide scientific oversight; 2) review all adverse effects or complications related to the study; 3) monitor accrual; 4) review summary reports relating to compliance with protocol requirements; and 5) provide advice on resource allocation. The DSMC will meet quarterly and as necessary by telephone. The recommendations of the DSMC will be reviewed and the PI will take appropriate corrective actions as needed.

DSMB: In addition to the internal DSMC, a DSMB will be established. The DSMB will be made up of professional with appropriate expertise, willing to participate, and who do not have any conflicts of interest. The DSMB will include the following: 1) two experts in the area of diabetes, 2) a biostatistician with expertise in the conduct of clinical trials, and 3) two members with expertise in ethics and quality of life evaluation. The DSMB will meet annually. The DSMB will perform the following activities:

- 1) Review the research protocol and plans for data and safety monitoring.
- 2) Evaluate the progress of the interventional trial, including periodic assessments of data quality and timeliness, participant recruitment, accrual and retention, participant risk versus benefit, performance of trial sites, and other factors that can affect study outcome.

- 3) Monitors will also consider factors external to the study when interpreting the data, such as scientific or therapeutic developments that may have an impact on the safety of the participants or the ethics of the study.
- 4) Make recommendations to the internal DSMC, IRB, and funding I/C at NIH concerning continuation or conclusion of the trial.
- 5) Protect the confidentiality of the trial data and the results of monitoring.

The DSMB will have the authority to halt the trial if it perceives that harm is occurring due to the intervention. The DSMB will meet with the internal DSMC yearly to review adverse events reports, patient complaints if any, and dropout rates. Data will be provided at these meetings by the investigators on key variables that may indicate harm, including changes in glycemic control, blood pressure, depression, and self-reported adherence to medication regimen. The DSMB biostatistician will evaluate confidentiality and integrity of the data base, and the procedures for recording and storing confidential files. The DSMB will also review the elements of the plan to deal with emergencies.

Institutional IRB: The IRB will review and approve the funded protocol, review patient consent forms, ensure protection of patient privacy and safety, and monitor the study on an ongoing basis. Adverse events will be reported to the IRB as they occur. Annual reports to the IRB will indicate accrual rate, adverse events, new findings that may influence continuation of the study, and reports of the DSMB.

E. INCLUSION OF WOMEN AND MINORITIES

INCLUSION OF WOMEN

Both men and women will be included in this study. Based on the demographics of the study clinics, we estimate that women will constitute 50% of the sample.

INCLUSION OF MINORITY GROUPS

Only minority adults (African Americans) are included in this study. This is justified because of the high burden of diabetes and its complication in African Americans, and the paucity of data on effective interventions in this population.

F. TARGETED/PLANNED ENROLLMENT TABLE

TARGETED/PLANNED ENROLLMENT: Number of Subjects - 200			
Ethnic Category	Sex/Gender		
	Females	Males	Total
Hispanic or Latino	0	0	0
Not Hispanic or Latino	100	100	200
Ethnic Category Total of All Subjects*	100	100	200
Racial Categories			
American Indian/Alaska Native	0	0	0
Asian	0	0	0
Native Hawaiian or Other Pacific Islander	0	0	0
Black or African American	100	100	200
White	0	0	0
Racial Categories: Total of All Subjects *	100	100	200

G. INCLUSION OF CHILDREN

Children (age <21) are excluded from this study. Children are excluded because type 2 diabetes is not common in children.

H. Resource Sharing Plans

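### Hypoglycaemia, a foreseeable harm of a glucose-lowering intervention, is named neither among the risks nor among the DSMB's harm variables, and is left to general adverse event reporting

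*Protocol*

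**What the plan says.** **Intended effect.** Aim 1 is to improve HbA1c in patients who enter with a value of 8% or more. Section 3 (Potential Benefits) expects the intervention to help patients by "improving blood glucose and blood pressure control". Section 4 (Importance of Knowledge) describes the FORA system as "providing reinforcement and positive feedback to patients that should increase adherence", without saying adherence to what.

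**Risks.** Section 1.c opens with "Potential risks to the patient include possible violation of the patient's privacy". It goes on to discomfort with the questionnaire and with blood draws, and ends with "discomfort with BP measurement, and psychological distress". Section 2.b (Protection against Risk) sets out protections for these and adds a general entry for unknown risks.

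**Harm data for the DSMB.** In Section 5 the investigators undertake to supply "key variables that may indicate harm, including changes in glycemic control, blood pressure, depression, and self-reported adherence to medication regimen". The DSMB also sees adverse event reports, patient complaints and dropout rates, reviews the plan for emergencies, and can stop the trial if it perceives that the intervention is causing harm.

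**General adverse event handling.** A medical monitor reviews every adverse event and reports to the IRB (Section 2.b, item B). The DSMC reviews adverse effects and meets quarterly. The DSMB meets annually and includes two diabetes experts (Section 5).

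**Contact and monitoring.** Under Description of Intervention, patients are "provided glucose test strips to allow testing at least once a day", and "The intervention will be delivered by telephone once a week for 12 weeks". The protocol describes nothing equivalent for usual care.

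**Questionnaires.** Section 1.b states: "The questionnaires will obtain information about demographics, clinical history, diabetes self-care, resource use, depression, and quality of life".

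**The concern.** An intervention designed to bring glucose down can bring it too low in some patients. The eligibility criteria do not restrict glucose-lowering drugs, so patients on drugs that can cause low glucose are not excluded. The event is foreseeable and is the natural counterpart of the intended benefit, yet neither the words hypoglycaemia or low glucose nor any equivalent appears in the protocol.

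Two things are at stake. First, the variables named for the DSMB could all look favourable while episodes became more frequent. Second, the DSMB must judge whether harm is due to the intervention, which calls for a comparison between arms. If episodes reach it only through general reporting, and one arm is tested and telephoned more often, an excess in that arm is hard to interpret. Events that were not asked about during follow-up cannot be recovered at analysis, so this cannot be left to the SAP.

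**Working it through.** The plan gives no figure on this point, so there is none to reproduce. The check sets the sections side by side.

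**Step 1: where each listed risk comes from (Section 1.c).**
- Loss of privacy: data handling.
- Discomfort with questions: study questionnaire.
- Discomfort and bleeding: blood draw.
- Discomfort with blood pressure measurement: study visit.
- Psychological distress: tied in Section 2.b to the depression questionnaire.

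All 5 of 5 arise from assessments or data handling, and 0 of 5 are consequences of the intervention's effect on glucose. In Section 2.b, raised blood pressure and a positive depression screen each have a stated referral route; low glucose has none. The unknown-risks entry does not fit, because this risk is foreseeable.

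**Step 2: what each named DSMB variable would show if glucose were lowered too far (Section 5).**
- Change in glycaemic control: the protocol's glycaemic outcome is HbA1c. It does not record episodes, and a fall would normally be read as benefit.
- Blood pressure: does not measure low glucose.
- Depression: does not measure low glucose.
- Self-reported medication adherence: a rise would normally be read as benefit.

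So 0 of 4 record low-glucose episodes directly. The two closest to the mechanism, HbA1c and adherence, would move in the favourable direction.

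**Step 3: ascertainment by arm.** Write the recorded episode rate in each arm as true rate × probability that an episode is noticed and reported. Then

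recorded ratio (TIDES / usual care) = true ratio × (detection in TIDES / detection in usual care).

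If the true ratio is 1, the recorded ratio equals the detection ratio alone. The protocol describes these opportunities for detection:
- TIDES only: glucose testing at least once a day, and 12 calls of about 30 minutes, or 12 × 30 = 360 minutes. The calls span 12 of about 52 weeks, or 23% of follow-up.
- Both arms: visits at baseline, 3, 6, 9 and 12 months. No common adverse event question is stated for them.

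The detection ratio may therefore exceed 1. The protocol gives no value for it and no hypoglycaemia rate, so neither the bias nor the number of episodes can be sized.

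**Step 4: what might already capture episodes in both arms.** The resource-use questionnaire may ask about emergency visits, and the clinical history or diabetes self-care items may touch on low glucose. The instruments are not shown, so this can be neither confirmed nor ruled out.

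**The case against.** The strongest reply is that nothing here is false or contradictory. Both lists are open, introduced by words such as include and including, and changes in glycaemic control can be read to cover low glucose. General adverse event review exists at three levels. The DSMB has two diabetes experts and reviews the monitoring plan, so it could itself ask for this variable. The questionnaires may already ask about emergency visits. The intervention is education, monitoring and activation, with no drug titration or glucose target stated, in patients who start at HbA1c of 8% or more.

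Most of this stands, and it limits the point. A reader might infer that hypoglycaemia is excluded from monitoring, or that the trial has no safety system for it. The text supports neither. A reader might also infer that detection bias will occur. The protocol shows unequal opportunity for detection, not its effect, and it leaves usual care undescribed.

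What does not stand is that this is merely unshown detail. The risk list and the DSMB variables belong to the protocol. It names four harm variables and omits the one most closely tied to the intended effect. Open wording allows hypoglycaemia to be added but does not ensure that it is asked about, or asked about alike in both arms.

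**Conclusion.** The point holds as a cheap safety improvement. Hypoglycaemia is absent from all 5 listed risks and all 4 named DSMB variables. It is left to general reporting, which may detect more episodes in TIDES.

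The size of the risk is unknown, because the protocol gives neither an event rate nor the proportion of patients on drugs that cause low glucose. HbA1c at 12 months, the secondary outcomes, the sample size and the efficacy conclusions are unaffected. The conclusion assumes that the daily testing and weekly calls are not also given in usual care, where nothing of the kind is described, and that the unseen questionnaires do not already contain equivalent questions.

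A reader might hope that common questions would give the DSMB a formal test or a count at which to act. The documents do not support setting one: with no event rate, any threshold would rest on assumed counts and on the choice of method. The comparison would be mainly descriptive.

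**What to change.** 1. Add hypoglycaemia to Potential Risks (Section 1.c) and to the harm variables supplied to the DSMB (Section 5).
2. At the existing 3-, 6-, 9- and 12-month visits, ask the same short questions in both arms about the period since the last visit: any low-glucose episode; any that needed another person's help; any that led to an emergency visit. Omit the third if the resource-use questionnaire already asks it.
3. Give the DSMB a descriptive table by arm of severe episodes (another person's help or an emergency visit), which depend less on having a meter. Report any-episode counts by arm with the caveat that identical questions do not equalise detection of mild episodes.
4. List events found through FORA readings or education calls separately, without comparing arms.

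The cost is at most 3 questions × 4 visits = 12 answers per patient, plus one DSMB table. No visits, staff or patients are added, and the endpoint and primary analysis do not change. The downsides are a slightly longer questionnaire, a mainly descriptive comparison, and residual detection bias for mild episodes.
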